- 5) Pregnancy: If participant indicates she is pregnant or has a positive pregnancy test at any session, she will be withdrawn from the study, and this event will remain open until delivery. At that time the medical monitor will contact the participant to ask a few questions about the baby's health and will update the open 'Medical Event Form'.

The following will be monitored and can lead to the participant being withdrawn by the PI or medical monitor:

- 1) Any hospitalization or debilitation in which participation in the study could be detrimental to the recovery process. This will be self-reported by the participant and will be reviewed by the PI and medical monitor to determine whether continued participation in the study is appropriate.
- 2) If a participant is behaving in an inappropriate or threatening manner, admits to lying about eligibility criteria, including omitting previous medical diagnoses and medications, is participating in other research studies that could affect the primary outcome measures, or does not follow study instructions, then the PI can withdraw him or her at the PI's discretion.

Serious adverse events (SAEs): Information about all serious adverse events will be collected and recorded on a standard Serious Adverse Event Report Form. A serious adverse event is an undesirable sign, symptom or medical condition which:

1. is fatal or life-threatening
2. requires or prolongs hospitalization
3. results in persistent or significant disability/incapacity
4. constitutes a congenital anomaly or a birth defect
5. is medically significant, in that it may jeopardize the subject and may require medical or surgical intervention to prevent one of the outcomes listed above.

A hospitalization would not be considered to be a serious adverse event if it is for the routine treatment or monitoring of the studied indication (smoking), not associated with any deterioration in condition, is treatment, which was elective or pre-planned, for a pre-existing condition unrelated to the indication under study and did not worsen, is admission to a hospital or other institution for general care, not associated with any deterioration in condition, is treatment on an emergency, outpatient basis for an event not fulfilling any of the definitions of serious given above, and not resulting in hospital admission.

Any SAE occurring after the participant has signed the informed consent and until the participant has stopped study participation must be reported. Investigator responsibilities for notification of SAEs are described above (see **Regulatory Issues** section).

Management of SAEs or Other Study Risks

The study medical monitor will review all AEs. A study participant may be discontinued from the study if the medical monitor and/or PI determines it is the best decision in order to protect the safety of a participant. In the event that a participant either withdraws from the study or is discontinued due to an AE/SAE, the participant will have appropriate follow-up medical monitoring until the problem resolves, stabilizes, or is clearly unrelated to the study medication. Any AE that remains open will be reviewed and closed at the last visit (R21 phase) or the last follow-up phone call (R33 phase).

Trial Efficacy

Plans for Interim Analysis of Efficacy Data

Data will be analyzed at the end of the R21 phase to determine if the results support moving to the R33 phase (i.e., if the go/no-go target has been met). No other interim analyses are planned.

DSM Plan Administration

Responsibility for data and safety monitoring

The PI ([name]) will be responsible for monitoring data integrity and participant's safety, executing the DSM plan and complying with the reporting requirements to the IRB, DSMB and NIDA. The PI will provide an annual summary of the Data Safety and Monitoring Board (DSMB) report to NIDA along with the progress report.

Frequency of DSM reviews

The PI and Research Assistant will meet at least weekly during the project, and the larger group (PI, Co-Investigators, Research Assistant and Data Manager) will meet at least monthly throughout the project. During these meetings, the progress of the trial, data quality, recruitment, retention, and other factors that may affect study outcomes will be reviewed. Adverse events will be reviewed to determine if there are any changes in participant risk. The investigators and staff are available to meet outside of the scheduled meetings, if concerns regarding a particular participant or another problem should arise.

The DSM Board will meet twice per year as described in the DSM Board section below.

Content of DSM report

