In Session 1 (pre-medication baseline), we will collect baseline measures of smoking urge, withdrawal symptoms, mood, cognitive performance, a behavioral economics-based measure of cigarette demand and effects of smoking a cigarette on cigarette reward, satisfaction and mood. Next, participants will be randomized to VAR (1 mg twice daily for 3 weeks) or PLA, using urn randomization to stratify on gender and dependence. Participants will complete a week of medication use using the standard dose run-up (0.5 mg once daily on days 1-3, 0.5 mg twice daily on days 4-7, then 1 mg twice daily until the end of the medication period). In Session 2, which occurs after one week on medication, participants will complete the same laboratory assessments as in Session 1. Next, participants will undergo a 3-day abstinence period. They will come to the laboratory twice per day and will receive escalating cash incentives for breath carbon monoxide (CO)-verified abstinence. At each visit, cigarette craving and withdrawal symptoms will be measured. At Session 8 (Thursday morning), participants who have been continuously abstinent will complete the same procedure as in Sessions 1. For ethical reasons, participants who complete the study through Thursday and who wish to remain abstinent may opt out of smoking during this session and will still receive full compensation for participation, as long as they attend this lab session and complete the other session measures.

Participants will be asked to return to the laboratory on Friday morning. Breath CO will be measured and time of first lapse (single cigarette) and relapse (return to regular smoking) will be collected among those who have lapsed and relapsed. Those still abstinent ($CO \leq 4$ ppm) since Session 8 will receive a small cash incentive. Next, participants will be shown how to use breath CO monitors with smart phones to record

and text us videos of themselves providing CO samples twice per day for the following week to determine time to lapse and relapse. Participants will receive \$5 for each submitted sample (not contingent on CO level), paid when the smart phone and CO monitor are returned at the end of the week.

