A total of 48 randomized participants are planned for the R21 phase. This sample size is based on Aim 1, which is to determine effects of VAR versus PLA on smoking urges and negative affect during abstinence, reinforcing effects of a smoking lapse, cognitive function and time to relapse in SS. A repeated-measures design with 48 total participants provides 80% power to detect main and interaction effects on the primary targets (smoking urges and negative affect during abstinence) and secondary targets (reinforcing effects of a smoking lapse) of at least $d = .40$ in size, assuming a moderate within-subject autocorrelation. While this effect size is somewhat smaller than those detected by West et al. (2008) for effects of abstinence on urges and negative affect during abstinence and smoking satisfaction and reward from relapse (d 's = .32-.44), abstinence was not controlled or biochemically verified after target quit date in that study, and, as the authors noted, it is possible that the effects that they observed were due only to those who were completely abstinent. With our rigorous control of abstinence, which includes twice-daily CO testing and a stringent abstinence criterion, we believe that we will detect smaller effects. We are not determining sample size based on Aim 2 (which is to examine the extent to which the effects of VAR on time to relapse are mediated through its effects on the target mechanisms), but we should be able to

detect medium-sized group effects on latency to second lapse, and estimate the size of mediation relationships that would be detectable as significant. We anticipate 20% attrition between enrollment and randomization. Therefore, we anticipate needing to enroll up to 60 participants (30 per group) to include 48 in the intent-to-treat sample.

R33 phase:

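### One R21 power figure (80% at d = .40, N = 48) covers several different tests, and no single correlation delivers it for all of them with d read as written

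*Combined protocol and SAP*

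**What the plan says.** The section Power Calculation and Sample Size, R21 phase, ties the sample size to the drug comparison: "This sample size is based on Aim 1, which is to determine effects of VAR versus PLA on smoking urges". It then says "A repeated-measures design with 48 total participants provides 80% power to detect main and interaction effects on the primary targets", extends this to the secondary targets (the reinforcing effects of a lapse), and sets the effect at d = .40 or more, "assuming a moderate within-subject autocorrelation". It gives no numerical correlation, no sidedness and no definition of d.

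The value .40 is set against a published study: "While this effect size is somewhat smaller than those detected by" that study, whose effects on urges, negative affect, and "smoking satisfaction and reward from relapse (d 's = .32-.44") are quoted. The same paragraph expects to "detect medium-sized group effects on latency to second lapse".

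The Data Analysis Plan, R21 phase, names different tests for these outcomes:

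- QSU and MNWS negative affect: GEE with AR(1) correlation, Group by Time, over Sessions 2-8.
- CEQ scales: mixed 2 x 2 ANOVA, Group by Abstinence, on Sessions 1 and 8. Participants who decline to smoke in Session 8 are left out.
- Latency: two-group t-test.

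Significance is p of .05 or less throughout. The Brief Description of Protocol adds two facts that matter for the CEQ: "In Session 1 (pre-medication baseline), we will collect baseline measures of smoking urge", and at Session 8 "participants who have been continuously abstinent will complete the same procedure as in Sessions 1".

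**The concern.** A seven-session group average, a two-session difference in change and a single-measure t-test have different variances, so one effect size and one N will not normally give them the same power. The CEQ is the sharpest case. Session 1 precedes medication, so a drug effect can appear only at Session 8. The interaction is therefore the informative test, and the Group main effect averages in a session in which no drug effect is possible.

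The CEQ scales and latency to relapse are listed among the primary outcome variables. If the stated sensitivity is too high, a null result on either could be read as evidence against varenicline from a study described as able to detect the effect. This bears on the interpretation of Aim 1 only. The rule for proceeding to the R33 phase is based on percentage reductions and does not depend on power.

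**Working it through.** **Inputs from the documents.** N = 48; d = .40; alpha .05; AR(1) over seven sessions for QSU/MNWS; two sessions for CEQ; t-test for latency. The enrolment target of 30 per group implies equal arms, so 24 per arm.

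**Assumptions, because the documents give no figure.** Correlations of .3, .5 and .7; two-sided testing (one-sided shown below); d in single-session SD units; d = .5 as a medium effect.

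**Method.** Let v be the variance of one participant's contrast in single-session SD units. The noncentrality is d² x 12 / v, since 24/2 = 12, referred to F with 1 and 46 df (critical value 4.05). Power of 80% needs noncentrality 8.19, so the detectable effect is √(8.19 v / 12) = 0.826 √v.

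- QSU/MNWS Group main effect: v = (1 + ρ)/(7 - 5ρ), the AR(1)-weighted mean of seven sessions.
- CEQ Group x Abstinence: v = 2(1 - r).
- CEQ Group main effect: v = (1 + r)/2.
- Latency: v = 1.

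**Reproducing the plan's figure.** For the QSU/MNWS Group main effect at ρ = .3, v = 1.3/5.5 = 0.236. The noncentrality is 0.16 x 12/0.236 = 8.12 and the power is 80%. The stated figure is therefore right for this test at that correlation.

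**All tests, two-sided:**

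| Test and effect | .3 | .5 | .7 | Correlation for 80% |
|---|---|---|---|---|
| QSU/MNWS Group, .40 SD | 80% | 65% | 49% | .295 or less |
| QSU/MNWS Group, .32 SD (lower cited value) | 61% | 47% | 34% | |
| CEQ Group x Abstinence, .40 SD difference in change | 21% | 27% | 42% | .883 |
| CEQ Group x Abstinence, f = .20 | 63% | 77% | 94% | .531 |
| CEQ Group, .40 SD on the Session 1/8 average | 39% | 35% | 31% | none (48% at r = 0) |
| CEQ Group, .40 SD at Session 8 only (.20 on the average) | 13% | 12% | 11% | none |

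As an example, CEQ Group x Abstinence at r = .5 has v = 1, noncentrality 0.16 x 12/1 = 1.92 and power 27%. In the f = .20 row each cell departs by .20 SD, so the difference in change is 4 x .20 = .80 SD, twice the nominal d.

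**One-sided .05, same correlations.**

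- QSU/MNWS Group: 88%, 76%, 62%.
- CEQ interaction at .40 SD: 31%, 39%, 55%; at f = .20: 75%, 86%, 97%.
- CEQ Group on the average: 52%, 47%, 43%.

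**QSU/MNWS Group x Time.** Power cannot be fixed, because the plan does not say what time pattern .40 describes. If the gap grows linearly from 0 at Session 2 to .40 SD at Session 8, power is 17-18% for a slope test and about 10% for the 6-df test. Read as f = .20 over seven equally correlated sessions (noncentrality .04 x 48 x 7/(1 - r), F with 6 and 276 df), it is 92% to over 99%. For a linear pattern at f = .20 under the planned AR(1) structure it is about 60%.

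**Latency.** At d = .5 the noncentrality is 0.25 x 12 = 3.0 and power is 40% (52% one-sided). Power of 80% needs d = 0.83.

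**Benchmark.** The midpoint of .32-.44 is .38. The chosen .40 lies inside the range and above its midpoint, so it is not smaller than the cited effects.

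**The case against.** The strongest reply is that the 80% can be recovered under fair readings.

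- **Different scales may have different correlations.** A value of .30 for QSU/MNWS and .53 for CEQ could both be called moderate, and with f = .20 the main effect and the CEQ interaction then both reach 80%. One-sided testing even gives an overlap at about .40-.44. This stands as far as it goes. However, the plan offers one correlation and states no one-sided test. The first reading also needs the closely spaced QSU/MNWS sessions to be less correlated than two CEQ sessions more than a week apart. The CEQ Group main effect stays below 50% two-sided and at 61% or less one-sided, for any non-negative correlation.
- **Read .40 as Cohen's f.** The QSU/MNWS Group, CEQ Group and CEQ interaction tests then all exceed 80% at correlations of .3-.7 (lowest 84%). But f = .40 is d = .80, and the text writes d and compares it with published d values of .32-.44.
- **Main effects may mean Abstinence.** With all 48 participants and a .40 SD change, the CEQ Abstinence effect has 77% power at r = .5 and 80% at r = .53. That is correct, but it is not the varenicline-versus-placebo contrast on which the sample size is said to rest.
- **The latency remark is hedged.** It carries no power figure, and the plan says Aim 2 does not set the sample size. It is a wording point, but the expectation is still too high.

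The plan's disclaimer about power for a pilot applies to the R33 phase only.

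**Conclusion.** The concern holds. The 80% is correct for the QSU/MNWS Group main effect if ρ is about .30 or less; there the fault is an unstated condition, not an error. It is not correct as a general statement for main and interaction effects on both target sets. A .40 SD drug effect on the CEQ has 21-42% power in the informative test at correlations of .3-.7, and the CEQ Group main effect stays below 50% two-sided. The QSU/MNWS interaction power is undetermined.

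These figures assume equal arms, two-sided .05, the correlations shown and all 48 participants. The CEQ figures are therefore optimistic: Session 8 data come only from continuous abstainers who agree to smoke, and the 20% attrition allowance covers only the period before randomization. Opt-outs may be few, since the plan reports one in the earlier study, but it gives no rate for failure to abstain.

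**What to change.** Keep N = 48 and the analyses. For each test, state the correlation, the sidedness and what d measures, including the time pattern meant by the QSU/MNWS interaction. Replace the single 80% with the effects detectable at 80% power (two-sided .05, 24 per arm):

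| Test | .3 | .5 | .7 |
|---|---|---|---|
| QSU/MNWS Group main effect (SD) | 0.40 | 0.48 | 0.58 |
| CEQ Group x Abstinence, difference in change (SD) | 0.98 | 0.83 | 0.64 |
| CEQ Group main effect, Session 1/8 average (SD) | 0.67 | 0.72 | 0.76 |
| Latency (d; no repeated measure) | 0.83 | 0.83 | 0.83 |

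Name the interaction as the CEQ test of varenicline. If the CEQ Group main effect is listed at all, say that it corresponds to 1.33, 1.43 and 1.52 SD at Session 8.

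Say that the CEQ figures worsen with loss before or at Session 8, and label any loss rate as an assumption. For example, losses of 10%, 20% and 30% leave 22, 19 and 17 per arm and give 0.86, 0.93 and 0.99 SD at r = .5.

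Reword the latency remark to refer to large effects (about d = 0.8), and describe .40 as within the cited range.

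The cost is text only. The one drawback is that the stated sensitivity becomes less favourable.

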Analyses will examine (1) the effects of the study conditions on smoking measures (CO levels, cigarettes per day) and the target mechanisms (craving and negative affect during abstinence, reinforcing effects of a smoking lapse, cognitive function); (2) the extent to which the effects of the treatment conditions on smoking are mediated through the effects on the target mechanisms; and (3) the feasibility and acceptability of a multi-week VAR + mCM intervention in SS.

Primary and Secondary Outcome Measures

Primary Outcome Variables:

- Primary target measures: Questionnaire on Smoking Urges (QSU) total score, Minnesota Nicotine Withdrawal Scale (MNWS) negative affect score (average of the anger, depression, anxiety and difficulty concentrating items).
- Secondary target measures: Cigarette Evaluation Questionnaire (CEQ) Satisfaction scale (mean of ratings on the satisfaction, taste and enjoyment items), Reward scale (mean of ratings on the calm, feel more awake, less irritable, help to concentrate and reduce hunger items), and Craving Reduction scale (single item).
- Latency to relapse (hours between the start of Session 8 and time of relapse, collected in person at Friday's session and by videoed CO sample in the follow-up week).

Secondary Outcome Variables:

- Expired breath carbon monoxide (CO) level
- Salivary cotinine level
- Cognitive performance measures (response times, errors of omission, errors of commission) on the WAIS-IV Coding task, Continuous Performance Test-3, 2-letter search task, WAIS-IV letter-number sequencing task, Wisconsin Card Sorting Task
- Diener and Emmons Mood Scales
- Cigarette Evaluation Questionnaire (CEQ) Enjoyment of Respiratory Sensations scale (single item) and Aversiveness scale (mean of ratings on the dizziness and nausea items).
- MNWS items not included in primary variables: insomnia, restlessness, increased appetite
- Demand indices on the Cigarette Purchase Task (CPT): intensity (consumption at zero price), Omax (maximum amount of money allocated to cigarettes), break-point (first price at which participant reports zero consumption) and Pmax (price at which Omax occurs).
- Other smoking measures: Fagerström Test for Nicotine Dependence (FTND), Smoking Stage of Change questionnaire, Contemplation Ladder
- Psychiatric symptom measures: Brief Psychiatric Rating Scale (BPRS), Calgary Depression Scale for Schizophrenia

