cognitive measure scores (with baseline scores covaried), CPT demand indices and within-session changes (post- minus pre-smoking) in CO level and positive and negative mood scale scores. Significant interactions will be followed by simple effects tests. Those who opt not to smoke in Session 8 will not be included in the Group x Abstinence analyses of CEQ, or pre-to-post smoking changes in CO or mood, but will be included in all other analyses (only one SS opted not to smoke in Session 8 in our previous study, Tidey et al., 2014). Latency to relapse will be defined as hours between the start of Session 8 and time of relapse, collected in person at Friday's session and by videoed CO sample in the follow-up week. We will follow up for one week after Friday's session, which is 8 days after Session 8. Thus, the maximum latency until second lapse will be 192 h, at which point data will be censored. Lapse latencies will be compared in VAR vs. PLA using a t-test. We will examine whether gender and FTND score (≤ 5 vs. ≥ 6) moderate the effects of VAR by adding these factors (separately) to each model.

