Mediation of the relationship between group and lapse latency will be examined using an SPSS macro (Preacher & Hayes, 2004). Hypothesized mediators will include baseline Calgary scale, cognitive performance and Contemplation Ladder scores, Session 8 QSU and MNWS scores, Session 8 CPT and CEQ Reward and Satisfaction scores, and Session 8 cognitive performance scores. Simple mediator models will be used to investigate the direct effect of medication on relapse latency (c path) with no mediator in the equation, as well as the medication \rightarrow mediator path (a), the mediator \rightarrow latency path (b), and the effect of medication on latency with the mediator in the equation (c' path). The indirect effect of medication on latency via each mediator ($c - c'$) is equal to the product of the coefficients of the "a" and "b" paths (i.e., "ab"). If ab is not normally distributed, 10,000 bootstrap resamples will be used to obtain lower and upper 95% confidence intervals (CI) for each indirect effect (Preacher & Hayes, 2008). All variables will be standardized first so that path coefficients can be directly compared across variables with different metrics. In addition, step-wise regression will be used to examine whether screening BPRS scores (entered in Step 1) and Session 8 BPRS scores (Step 2) predict latency to relapse. The SPSS mainframe statistical package (SPSS, Inc., Chicago, IL) will be used for GEE, mediation and regression analyses. All other analyses will be conducted using SPSS Statistics Version 20 for Windows (IBM, Armonk, NY). Differences will be considered significant when $p \leq .05$.

R33 phase

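### The R21 sample is said to be able to detect medium-sized effects on relapse latency, but the planned t-test has only about 40% power for such an effect

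*Combined protocol and SAP*

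**What the plan says.** Under Power Calculation and Sample Size, R21 phase: "A total of 48 randomized participants are planned for the R21 phase". The size is said to rest on Aim 1, which includes time to relapse. The section states that a repeated-measures design of this size "provides 80% power to detect main and interaction effects on the primary targets", and on the secondary targets, of at least d = .40. It then says that the sample was not sized for Aim 2 (mediation), but that the study should be able to "detect medium-sized group effects on latency to second lapse". No power, numeric effect size or standard deviation accompanies that clause.

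On numbers: "We anticipate 20% attrition between enrollment and randomization", and "we anticipate needing to enroll up to 60 participants (30 per group) to include 48 in the intent-to-treat sample". No allowance is made for loss after randomization.

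The primary outcome list includes "Latency to relapse (hours between the start of Session 8 and time of relapse". The R21 Data Analysis Plan fixes the test: "Lapse latencies will be compared in VAR vs. PLA using a t-test". It sets significance at the .05 level without saying whether tests are one- or two-sided, and it censors latency at 192 h.

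The terms second lapse, lapse latency and relapse latency are used for what the 192 h passage shows to be one measure. They should be reconciled.

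**The concern.** The 80% power at d = .40 belongs to outcomes measured repeatedly on each person. Latency is measured once, so its comparison is a plain between-group test on 48 people. A reader of the power section would nevertheless expect a medium effect on latency to be found if it exists.

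What is at stake is the reading of one primary outcome. If varenicline delayed relapse by a medium amount, the planned test would miss it about 6 times in 10. With the present sentence as the only statement on sensitivity for latency, a non-significant result could be taken as evidence that the drug does not delay relapse.

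**Working it through.** **Inputs from the document.** 48 randomized in two arms; equal enrolment (30 per group); two-sample t-test; significance at .05.

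**Assumptions, because the document does not state them.** 24 per arm (48/2); two-sided test; medium means d = .5; a latency is obtained for everyone randomized.

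**The plan's own figures.** The enrolment figure reproduces: 48/(1 - 0.20) = 60. There is no latency power figure to reproduce. The 80% at d = .40 concerns other outcomes and depends on a within-subject correlation described only as moderate, so it cannot be reproduced uniquely.

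**Formula.** For a t-test with n per arm, power comes from the noncentral t distribution with df = 2n - 2 and noncentrality d × √(n/2).

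**Power for a medium effect.**
- n = 24: df = 46, two-sided critical value 2.013.
- Noncentrality = 0.5 × √12 = 1.732.
- Power = 39.6% (41.0% by the normal approximation).

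**Effect detectable with 80% power at 24 per arm.** Solving for d gives 0.826, with noncentrality 0.826 × √12 = 2.86.

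**Sample needed for 80% power at d = .5.** 63 per arm gives 79.5% and 64 gives 80.1%, so 64 per arm, or 128 in total.

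**Power by effect size, 24 per arm, two-sided .05.**

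| d | Power |
|---|---|
| 0.4 | 27% |
| 0.5 | 40% |
| 0.6 | 53% |
| 0.7 | 66% |
| 0.8 | 77% |

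**Other readings of the unstated inputs, varied one at a time.**

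| Reading | Power |
|---|---|
| One-sided .05, d = .5, 24 per arm | 52% |
| All 60 enrolled analysed (30 per arm), d = .5 | 48% |
| Medium as r = .3, i.e. d = 2 × 0.3/√(1 - 0.09) = 0.63, 24 per arm | 57% |

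**Fewer latencies than 24 per arm.** The latency clock starts at Session 8, and the brief protocol description has that session's procedure completed by participants who have been continuously abstinent. Some randomized participants may therefore have no latency. The document gives no figure for this. With an assumed 20 per arm, power at d = .5 is 34%; with an assumed 16 per arm, it is 28%.

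**The case against.** The strongest defence is that the sentence is a hedged expectation, not a calculated claim. It carries no power level, it sits in a sentence that opens by saying Aim 2 did not set the sample size, and d = .5, two-sided testing and 24 per arm are all supplied by the reader. This stands in part: the fault is an unsupported statement, not a miscalculated number. It does not remove the fault. Time to relapse belongs to Aim 1, the stated basis of the sample size. Varying the unstated inputs one at a time never lifts power above 57%. The caveat about limited power is given only for the R33 phase.

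A second defence is that no decision depends on latency. This stands. The go/no-go rule uses a reduction of at least 20% in the primary or secondary targets in at least half the sample, so a null latency result cannot block the move to R33.

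Three stronger readings are tempting, and the document does not support them:
- *A null latency result will be misread.* The plan does not say how such a result would be interpreted. Misreading is a risk that the text leaves open, not a planned step.
- *The mediation analysis fails with the group comparison.* The plan assesses mediation through the indirect effect and does not make a significant total effect a condition. It promises only to estimate the size of the mediation relationships.
- *Only large effects can be detected.* That holds only at 80% power, a level the plan does not attach to latency. Smaller effects are detectable with lower probability, as the table shows.

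**Conclusion.** The statement on latency is not supported by the planned analysis. Under the assumptions listed, power for a medium effect is about 40%, against the 80% that the same section uses for its other outcomes, and 80% power requires d of about .83. The plausible alternative readings give 48% to 57%. The 40% figure is more likely optimistic than pessimistic, because it assumes a latency for all 48.

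This should be fixed, but it is not critical. It changes no test, endpoint, sample size or go/no-go criterion. Its effect is confined to how a non-significant result on one primary outcome is read.

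**What to change.** Replace the latency clause in the R21 sample-size section with wording such as: *With 24 per arm, the t-test of latency has 80% power only for d of about .83; power for d = .5 is about 40%.* State there that the test is two-sided, if that is intended.

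In the R21 Data Analysis Plan, add that the group difference in latency will be reported with a 95% CI, and that a non-significant result will not be taken as evidence of no effect. Use one term for the measure throughout.

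The cost is a few sentences and a less favourable stated figure. Enrolment does not change.
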